Ab=antibody; ADE=adverse device effect; AE=adverse event; BKZ=bimekizumab; BSA=body surface area; CT=computed axial tomography; DLQI=Dermatology Life Quality Index; ECG=electrocardiogram; eCRF=electronic Case Report Form; HBcAb=anti-hepatitis B core antibody; HBsAg=hepatitis B surface antigen; HBV=hepatitis B virus; HCV=hepatitis C virus; HIV=human immunodeficiency virus; IGA=Investigator's Global Assessment; IGRA=interferon-gamma release assay; IMP=investigational medicinal product; IRT=interactive response technology; P-SIM=Psoriasis Symptom and Impact Measure; PASI=Psoriasis Area and Severity Index; PEOT=Premature End of Treatment; PSD=Patient Symptom Diary; Q4W=every 4 weeks; Q8W=every 8 weeks; scalp IGA=scalp-specific IGA; SFU=Safety Follow-Up; TB=tuberculosis

Note: All assessments should be performed prior to IMP administration. The IMP administration is the starting point for the next administration period. Thus, the assessments in Week 16 and Week 32 belong to the previous treatment period.

^a For visits from the first dose of IMP through Week 32, the visit window is ± 4 days from the scheduled visit. For the SFU Visit, the visit window is ± 7 days from the scheduled visit.

^b The SFU Visit will occur 17 weeks after the final dose of IMP.

^c Ensure no significant changes in medical history.

^d Includes evaluation of signs and symptoms of active TB and risk for exposure to TB.

^e The physical examination will be performed as described in Section 8.2.3.

^f Vital signs (sitting systolic and diastolic blood pressure, pulse rate, and body temperature) are to be measured prior to blood sampling and prior to dosing, where applicable.

^g Pregnancy testing will consist of serum testing at Screening. A urine pregnancy test will be administered at all other visits.

^h Study participants who have evidence of or test positive for hepatitis B or C are excluded from the study, per Exclusion Criterion #9 (Section 5.2). A positive test for HBV is defined as: 1) positive for HBsAg or 2) positive for HBcAb. A positive test for HCV is defined as: 1) positive for anti-HCV Ab and 2) positive via a confirmatory test for HCV (eg, HCV polymerase chain reaction).

ⁱ The HIV test results will not be recorded in the eCRF.

^j Screening chest x-ray/CT scan must occur within 3 months prior to Screening Visit.

Table 1-1: Schedule of Activities

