5.2 Exclusion criteria

Study participants are not permitted to enroll in the study if any of the following criteria are met:

1. Female study participant who is breastfeeding, pregnant, or plans to become pregnant during the study or within 17 weeks following the final dose of IMP.
2. Study participant previously participated in a bimekizumab clinical study and received ≥ 1 dose of the IMP (including placebo).
3. Study participant previously participated in another study of a medication (systemic) under investigation within the last 12 weeks or at least 5 half-lives relative to Baseline, whichever is greater, or is currently participating in another study of a medication (systemic) under investigation.
4. Study participant previously participated in another study of a topical medication under investigation within the last 4 weeks relative to Baseline or is currently participating in another study of a topical medication under investigation.

5. Study participant previously participated in another study of a medical device under investigation within the last 4 weeks relative to Baseline or is currently participating in another study of a medical device under investigation.
6. Study participant has a known hypersensitivity to any excipients of bimekizumab.
7. Study participant has a form of PSO other than chronic plaque-type (eg, pustular, erythrodermic, guttate, or drug-induced PSO).
8. Study participant has an active infection or history of infection(s) as follows:
 - Any active systemic infection (except common cold) within 14 days prior to Baseline.
 - A serious infection, defined as requiring hospitalization or intravenous anti-infectives within 2 months prior to the first dose of IMP.
 - Recurrent or chronic infections that, in the opinion of the Investigator, might cause this study to be detrimental to the study participant.
 - Known history of opportunistic infections. Opportunistic infections are infections caused by uncommon pathogens (eg, pneumocystis carinii, cryptococcosis) or unusually severe infections caused by common pathogens (eg, cytomegalovirus, herpes zoster, candida).
9. Study participant has concurrent acute or chronic viral hepatitis B or C or human immunodeficiency virus (HIV) infection. Study participants who have evidence of, or tested positive for, hepatitis B or hepatitis C are excluded.

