 - A positive test for the hepatitis B virus (HBV) is defined as: 1) positive for hepatitis B surface antigen (HBsAg+), or 2) positive for anti-hepatitis B core antibody (HBcAb+).
 - A positive test for the hepatitis C virus (HCV) is defined as: 1) positive for hepatitis C antibody (anti-HCV Ab), and 2) positive via a confirmatory test for HCV (for example, HCV polymerase chain reaction).
10. Study participant has received any live (includes attenuated) vaccination within the 8 weeks prior to Baseline (eg, inactivated influenza and pneumococcal vaccines are allowed, but nasal influenza vaccination is not permitted).
11. Study participant has received Bacillus Calmette-Guerin vaccinations within 1 year prior to IMP administration.
12. Study participant has known TB infection, is at high risk of acquiring TB infection, or has current or history of nontuberculous mycobacterium (NTMB) infection. A study participant newly diagnosed with LTBI as a result of a positive IGRA screening test may be rescreened once and enrolled after receiving ≥ 4 weeks of appropriate LTBI therapy, after consultation with the Medical Monitor, and if no evidence of therapy-related hepatotoxicity has occurred prior to the first injection (alanine aminotransferase [ALT]/aspartate aminotransferase [AST] remain ≤ 2 times upper limit of normal [ULN]).

Study participant has a past history of active TB involving any organ system unless adequately treated according to World Health Organization/Center for Disease Control and Prevention therapeutic guidance and is proven to be fully recovered upon consult with a TB specialist.

Refer to Section 8.2.5.2 for details on TB assessments to be performed at Screening.

13. Study participant has a history of a lymphoproliferative disorder, including lymphoma or current signs and symptoms suggestive of lymphoproliferative disease.
14. Study participant has any active malignancy or history of malignancy within 5 years prior to the Screening Visit EXCEPT treated and considered cured cutaneous squamous or basal cell carcinoma, in situ cervical cancer, or ductal carcinoma in situ of the breast.
15. Study participant has a diagnosis of inflammatory conditions other than PSO vulgaris or PSA, including, but not limited to, rheumatoid arthritis, sarcoidosis, inflammatory bowel disease, or systemic lupus erythematosus.

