8.2 Safety assessments

8.2.1 Clinical safety laboratory assessments

All protocol-required laboratory assessments, as defined in Section 10.2 (Appendix 2) must be conducted in accordance with the laboratory manual and the SoA (Table 1-1). See Section 10.2 and the SoA for the list, timing, and frequency of clinical laboratory tests to be performed. Blood samples will be collected prior to dosing for measurement of hematology and biochemistry laboratory measurements as well as interferon-gamma release assay (IGRA) assessments (see Section 8.2.5.3.4) as specified in the SoA (Table 1-1).

The Investigator must review the laboratory report, document this review, and record any clinically significant changes occurring during the study in the AE section of the eCRF. The laboratory reports must be filed with the source documents. Clinically significant abnormal laboratory findings are those which are not associated with the underlying disease, unless judged by the Investigator to be more severe than expected for the study participant's condition.

All laboratory tests with values considered clinically significantly abnormal during participation in the study or within 17 weeks after the final dose of IMP should be repeated until the values return to normal or Baseline or are no longer considered clinically significant by the Investigator or Medical Monitor. If such values do not return to normal/Baseline within a period of time judged reasonable by the Investigator, the etiology should be identified and the Sponsor notified.

If laboratory values from nonprotocol-specified laboratory assessments performed at the institution's local laboratory require a change in study participant management or are considered clinically significant by the Investigator (eg, SAE or AE or dose modification), then the results must be recorded in the eCRF.

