10.2 Appendix 2: Clinical laboratory tests

- The tests detailed in [Table 10-1](#) will be performed by the central laboratory, with the exception of urine dipsticks and urine pregnancy tests, which will be performed locally at the site.
- Local laboratory results are only required in the event that the central laboratory results are not available in time for either IMP administration and/or response evaluation. If a local sample is required, it is important that the sample for central analysis is obtained at the same time. Additionally, if the local laboratory results are used to make either an IMP decision or response evaluation, the results must be entered into the eCRF.
- Protocol-specific requirements for inclusion or exclusion of study participants are detailed in [Section 5.1](#) and [Section 5.2](#), respectively.
- Additional tests may be performed at any time during the study as determined necessary by the Investigator or required by local regulations.

Table 10-1: Protocol-required safety laboratory assessments

Laboratory assessments	Parameters			
Hematology	Platelet count	RBC indices: MCV MCH MCHC		WBC count with differential: Neutrophils Lymphocytes Monocytes Eosinophils Basophils
	RBC count			
	Hemoglobin			
	Hematocrit			
Clinical chemistry ^a	BUN	Potassium	AST	Total bilirubin
	Creatinine	Sodium	ALT	Glucose (nonfasting)
	Calcium	Alkaline phosphatase	Lipid panel	Chloride
		GGT	LDH	
Routine urinalysis	
Specific gravitypH, glucose, protein, blood, ketones, bilirubin, urobilinogen, nitrite, leukocyte esterase by dipstickMicroscopic examination (if protein, blood, nitrite, or leukocyte esterase is abnormal)			
Other Screening tests	
Serum hCG pregnancy test (as needed for WOCBP) by central laboratory at Screening and urine pregnancy test locally for all assessments after ScreeningIGRA testingUrine drug screenSerology (HIV antibody, HBsAg, and hepatitis C virus antibody) 
Specific details regarding the handling and processing of serum chemistry, hematology, and urinalysis samples are provided in the study laboratory manuals.
 
All study-required laboratory assessments will be performed by the central laboratory, with the exception of urine dipsticks and urine pregnancy tests, which will be performed locally at the site.
 
The results of each test must be entered into the eCRF.
			

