ALT=alanine aminotransferase; AST=aspartate aminotransferase; BUN=blood urea nitrogen; eCRF=electronic Case Report Form; GGT=gamma glutamyltransferase; HBsAg=hepatitis B surface antigen; hCG=human chorionic gonadotropin; HIV=human immunodeficiency virus; IGRA=interferon-gamma release assay; INR=international normalized ratio; LDH=lactate dehydrogenase; MCH=mean corpuscular hemoglobin; MCHC=mean corpuscular hemoglobin concentration; MCV=mean corpuscular volume; RBC=red blood cell count; ULN=upper limit of normal; WBC=white blood cell count; WOCBP=woman of childbearing potential

^a Details of liver chemistry stopping criteria and required actions and follow-up assessments after liver stopping or monitoring event are provided in Section 7.1.1 and Appendix 6 (Section 10.6). All events of ALT $\geq 3 \times$ ULN and bilirubin $\geq 2 \times$ ULN ($>35\%$ direct bilirubin) or ALT $\geq 3 \times$ ULN and INR >1.5 , if INR measured, may indicate severe liver injury (potential Hy's Law) and must be reported as an SAE.

Investigators must document their review of each laboratory safety report.

Laboratory/analyte results that could unblind the study will not be reported to investigative sites or other blinded personnel until the study has been unblinded.

PUBLIC COPY

This document cannot be used to support any marketing authorization application and any extensions or variations thereof.

10.3 Appendix 3: Adverse events – Definitions and procedures for recording, evaluating, follow up, and reporting

Definition of AE

AE definition

 An AE is any untoward medical occurrence in a patient or clinical study participant, temporally associated with the use of IMP, whether or not considered related to the IMP. NOTE: An AE can therefore be any unfavorable and unintended sign (including an abnormal laboratory finding), symptom, or disease (new or exacerbated) temporally associated with the use of IMP.

Events meeting the AE definition

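### The screening serology in Protocol Table 10-1 omits hepatitis B core antibody, a marker that exclusion criterion 9 and Schedule of Activities footnote h make exclusionary

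*Protocol*

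**What the plan says.** **Eligibility rule.** Protocol Section 5.2, criterion 9, states: "Study participants who have evidence of, or tested positive for, hepatitis B or hepatitis C are excluded". It then defines a positive hepatitis B test by two alternatives. One is HBsAg; the other begins "positive for anti-hepatitis B core antibody (HBcAb" (cut here before the plus sign and closing bracket). Either is enough to exclude.

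**Schedule of Activities.** Table 1-1 has a Screening row for hepatitis B and C testing. Its footnote h refers to criterion 9 and repeats the rule: "A positive test for HBV is defined as: 1) positive for HBsAg or 2) positive for HBcAb".

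**Laboratory panel.** Section 8.2.1 says: "All protocol-required laboratory assessments, as defined in Section 10.2 (Appendix 2) must be conducted in accordance with the laboratory manual and the SoA". In Section 10.2, the serology line under the other screening tests of Table 10-1 names "HIV antibody, HBsAg, and hepatitis C virus antibody". The same table adds: "All study-required laboratory assessments will be performed by the central laboratory", apart from urine dipsticks and urine pregnancy tests.

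**The concern.** The eligibility rule needs two hepatitis B markers, and the table presented as the list of required tests supplies one. Section 5 permits no eligibility waivers. Section 8 requires the screening evaluations to confirm every criterion before randomisation. A criterion that depends on a test missing from the required list cannot be confirmed from that list.

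What is at stake is whether an exclusion the sponsor chose to write is applied evenly, or at all for one of its two markers. The sponsor names liver function changes among its safety topics of interest (Sections 2.3 and 8.3.7), so this bears on participant safety as well as on eligibility deviations.

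**Working it through.** No arithmetic applies, because the plan states no figure on this point. The check sets every place that mentions hepatitis B testing side by side.

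| Place in the protocol | HBsAg | HBcAb | Purpose |
|---|---|---|---|
| Section 5.2, criterion 9 | yes | yes | eligibility |
| Table 1-1, footnote h | yes | yes | Screening test row |
| Table 10-1, serology line | yes | **no** | required screening panel |
| Table 10-4 | yes | IgM form only | work-up after a suspected liver injury |

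1. **Markers needed against markers listed.** The rule uses 2 markers and Table 10-1 lists 1 of them.

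2. **Who falls through the gap.** There are four possible marker combinations. Both HBsAg-positive combinations are caught by either version of the panel. A candidate negative on both is eligible on this point under either version. The fourth, HBsAg negative and HBcAb positive, meets criterion 9 but passes the Table 10-1 serology. The conflict is confined to that one group.

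3. **Is the omission a loss in text extraction?** It does not look like one. The serology line is a complete bracketed list. The table's abbreviation list runs "GGT=gamma glutamyltransferase; HBsAg=hepatitis B surface antigen; hCG=human chorionic gonadotropin", with no entry for HBcAb where alphabetical order would place it. The abbreviation list under Table 1-1 defines both markers.

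4. **Does another laboratory table supply the test?** No. Table 10-4 names a core-antibody test only in its IgM form, and only for investigating a liver event after it has occurred. It is not a screening test.

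5. **Does the allowance for additional tests close the gap?** No. Section 10.2 lets the investigator add tests judged necessary, or tests that local regulation requires. That is a discretion, whereas criterion 9 applies to every candidate.

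6. **Is there other evidence that Table 10-1 was not aligned with the footnotes?** Yes. The table requires the result of each test to be entered in the eCRF, while footnote i of Table 1-1 says HIV results will not be recorded there.

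**The case against.** The strongest reply is that the protocol does call for HBcAb elsewhere. Footnote h hangs on a scheduled Screening test. Section 8.2.1 points to the Schedule of Activities and the laboratory manual as well as to Section 10.2. Section 8 makes adherence to the schedule mandatory. Section 10.2 itself refers the reader back to Sections 5.1 and 5.2 for eligibility requirements. A site or laboratory reading all of these together would test both markers. This stands, and it limits the finding to conflicting instructions. It does not remove the conflict, because Section 8.2.1 uses Section 10.2 to define the required assessments and that definition is one marker short.

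A reader might infer more than the documents support, in four ways.

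- **That the test was never run.** The laboratory manual is not available, and the laboratory may have been set up correctly.
- **That a number of breaches can be estimated.** The documents give no HBcAb prevalence. Any count would also have to assume that nobody was tested.
- **That the Per-Protocol Set is altered.** Protocol Section 9.1 and SAP Section 3 remove only important deviations affecting the co-primary endpoints, and nothing in the documents links HBcAb status to PASI90 or IGA 0/1. An undetected breach would not be removed in any case. The primary analysis uses the Randomized Set.
- **That hepatitis C has the same fault.** The hepatitis C antibody test is listed. The confirmatory test matters only after a positive antibody result, so leaving it off a routine panel is not a contradiction.

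**Conclusion.** The contradiction is real and lies in an operative screening table. Table 10-1 lists one of the two hepatitis B markers that criterion 9 and footnote h use to exclude. Its consequence depends on one fact outside the documents, namely how the central laboratory was set up.

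- If it was set up from Table 10-1 alone, every HBsAg-negative, HBcAb-positive candidate who was otherwise eligible could have been randomised against criterion 9.
- If it followed footnote h, none were missed on this account.

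The size is therefore unknown, with zero as a possible value. The documents show no effect on Type I error, power, sample size or the primary analysis. The point is worth correcting because it concerns participant safety and the even application of an exclusion, and because the correction is cheap.

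**What to change.** 1. Reconcile criterion 9, footnote h of Table 1-1 and the serology line of Table 10-1, so that the eligibility rule and the required screening panel name the same hepatitis B markers. Which markers the rule should use is for the sponsor's clinical team to decide; this review takes no position.
2. Confirm from the laboratory manual and the central laboratory's set-up which hepatitis B markers were actually run at Screening.
3. Check that each randomised participant has a result for every marker the reconciled rule uses, and record any gap or breach as an eligibility deviation.

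The cost is a change of table wording, a check of the laboratory set-up and a review of existing screening results. If the reconciled panel tests a marker that was not being run, there may be more screen failures.
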